### **15.4 Reporting of Safety Issues and Serious Breaches of the Protocol or ICH GCP**

In the event of any prohibition or restriction imposed (i.e., clinical hold) by an applicable Competent Authority, or if the investigator is aware of any new information which might influence the evaluation of the benefits and risks of the investigational product, the sponsor should be informed immediately.

In addition, the investigator will inform the sponsor immediately of any urgent safety measures taken by the investigator to protect the study subjects against any immediate hazard, and of any serious breaches of this protocol or of ICH GCP that comes to the attention of the investigator.

### **15.5 Subject Confidentiality**

All parties will ensure protection of subject personal data and will not include subject names on any sponsor forms, reports, publications, or in any other disclosures, except where required by law. In case of data transfer, the sponsor will maintain high standards of confidentiality and protection of subject personal data.

The sponsor and designees affirm and uphold the principle of the subject's right to protection against invasion of privacy. Throughout this study, a subject's source data will only be linked to the sponsor's clinical study database or documentation via a unique identification number. As permitted by all applicable laws and regulations, limited subject attributes, such as sex, age, or date of birth, and subject initials may be used to verify the subject and accuracy of the subject's unique identification number.

To comply with ICH Guidelines for GCP and to verify compliance with this protocol, the sponsor requires the investigator to permit its monitor or designee's monitor, representatives from any regulatory authority (eg, US FDA), the sponsor's designated auditors, and the appropriate IRBs and IECs to review the subject's original medical records (source data or documents), including, but not limited to, laboratory test result reports, ECG reports, admission and discharge summaries for hospital admissions occurring during a subject's study participation, and autopsy reports. Access to a subject's original medical records requires the specific authorization of the subject as part of the informed consent process.

Copies of any subject source documents that are provided to the sponsor must have certain personally identifiable information removed (i.e., subject name, address, and other identifier fields not collected on the subject's CRF).

## **16 PUBLICATION OF STUDY RESULTS**

No publication or disclosure of study results will be permitted, except under the terms and conditions of a separate, written agreement between sponsor and the investigator and/or the investigator's institution. The sponsor must have the opportunity to review and approve all proposed abstracts, manuscripts, or presentations regarding this study prior to submission for publication/presentation. Any information identified by the sponsor as confidential must be deleted prior to submission.

For all publications relating to the study, the institution will comply with recognized ethical standards concerning publications and authorship, including: Section II - "Ethical Considerations in the Conduct and Reporting of Research" of the Uniform Requirements for Manuscripts Submitted to Biomedical Journals, <http://www.icmje.org/index.html#authorship>, established by the International Committee of Medical Journal Editors.

## Appendix A: Schedule of Activities

Please refer to [Section 9.2](#) for detailed information regarding the study procedures and evaluations, and please refer to [Section 9.3](#) for detailed information regarding the activities to be performed at each study visit.

	Screening	Primary efficacy period (blinded, fixed-dose treatment) (Day 1-Week 6)					Blinded dose adjustment, data cleaning period (Week 7-10)	Open-label extension period (Week 11-16)		Safety Follow-up (Week 17-18)
Study Week	-4 to 0	Base line	1	2	4	6	10 (EOT, Blinded Period)	14	16 (EOT, Open-Label Period)	18
Study Day	-28 to -4	1	8	15	29	43	71	99	113	127
Visit Window (Days)			±1	±1	±3	±3	±3	±3	±3	±3
Informed consent	X									
Review inclusion/exclusion criteria	X	X								
Individual subject data lock (for subjects who complete Week 6)							X			
Individual subject unblinding (for subjects who complete Week 6)							X			
Demographics, medical history, physical exam, and weight	X									
Vital signs	X	X	X	X	X	X	X	X	X	X
12-lead electrocardiogram		X								
Adverse event review			X	X	X	X	X	X	X	X
Concomitant medication review	X	X	X	X	X	X	X	X	X	X
Serum pregnancy test	X								X	
Urine pregnancy test		X								
Coagulation tests		X								

	Screening	Primary efficacy period (blinded, fixed-dose treatment) (Day 1-Week 6)					Blinded dose adjustment, data cleaning period (Week 7-10)	Open-label extension period (Week 11-16)		Safety Follow-up (Week 17-18)
Study Week	-4 to 0	Base line	1	2	4	6	10 (EOT, Blinded Period)	14	16 (EOT, Open-Label Period)	18
Study Day	-28 to -4	1	8	15	29	43	71	99	113	127
Visit Window (Days)			±1	±1	±3	±3	±3	±3	±3	±3
Folate and vitamin B12	X									
Hb using HemoCue® (Week 10 assessment is not for subjects who discontinue prior to Week 6)			X	X	X	X	X	X		
Complete blood count, including Hb [a]	X	X	X	X	X	X	X	X	X	X
Serum chemistry and eGFR	X	X		X	X	X	X	X	X	X
Iron indices	X	X		X	X	X	X		X	
Hepcidin		X				X	X			X
C-reactive protein		X				X	X			X
VEGF		X				X	X			X
PK pre-dose sample (study drug to be administered after sample collection)					X					
Blinded study drug dispensation, as necessary		X		X	X	X				
Blinded study drug dosing		Blinded study drug dosing								
Vadadustat dispensation, as necessary [b]							X	X		
Vadadustat dosing [b]								Open-label vadadustat dosing		
Study drug compliance check			X	X	X	X	X	X	X	

Abbreviations: eGFR, estimated glomerular filtration rate; EOT, end of treatment; Hb, hemoglobin; PK, pharmacokinetics; VEGF, vascular endothelial growth factor

- [a] For subjects who discontinue study drug due to an excess Hb response, blood samples will be collected weekly to monitor Hb until the subject no longer exhibits an excess Hb response. The blood samples will be analyzed in a lab. Point-of-care Hb assessment will not be used for such evaluations.
- [b] Subjects who were randomized to receive vadadustat treatment during the primary efficacy period and complete the Week 10 visit will continue to the open-label extension period.

## Appendix B: Japanese Society of Nephrology 2009 Equation to Calculate eGFR

The estimated glomerular filtration rate (eGFR) will be calculated from serum creatinine using the 2009 Japanese Society of Nephrology Equation (3-variables; [Matsuo 2009](#)).

$$\text{eGFR (mL/min/1.73 m}^2\text{)} = \mathbf{194} \times (\text{S}_{\text{cr}} \text{ in mg/dL})^{-1.094} \times (\text{Age})^{-0.287} \times (0.739 \text{ if female})$$

## 2 PROTOCOL SYNOPSIS

Study Title	Phase 2, Randomized, Double-Blind, Placebo-Controlled, Dose-Finding Study to Assess the Efficacy, Safety, Pharmacokinetics, and Pharmacodynamics of Vadadustat in Japanese Subjects with Anemia Secondary to Non-Dialysis Dependent Chronic Kidney Disease
Protocol Number	AKB-6548-CI-0021
Study Phase	Phase 2
Investigational Product	Vadadustat; each tablet contains 150 mg of vadadustat for oral administration
Study Population	The study population will consist of male and female Japanese adults aged 20 years or older with anemia secondary to non-dialysis dependent chronic kidney disease (NDD-CKD) who are not currently being treated with an erythropoiesis-stimulating agent (ESA)
Investigative Sites	Approximately 25 sites in Japan
Planned Number of Subjects	Approximately 48 subjects will be enrolled in the study, with 36 subjects receiving one of the 3 doses of vadadustat and 12 subjects receiving placebo: 

• 150 mg vadadustat once daily (n=12)

• 300 mg vadadustat once daily (n=12)

• 600 mg vadadustat once daily (n=12)

• Placebo (n=12)

Study Objectives	

• Primary Objective: To assess the dose-response relationship between oral vadadustat once daily (QD) dosing for 6 weeks and the change in hemoglobin (Hb) in Japanese subjects with anemia secondary to NDD-CKD; in order to define the starting dose for use in Phase 3 clinical studies in Japan

• Secondary Objectives:

- To assess the safety, tolerability, pharmacokinetics (PK), and pharmacodynamics (PD) of oral vadadustat QD dosing in Japanese subjects with anemia secondary to NDD-CKD during the 6-week, primary efficacy period

- To evaluate the effect of dose adjustments and demonstrate the maintenance effect on Hb during a 10-week maintenance period

Study Design Overview	This is a Phase 2, randomized, double-blind, placebo-controlled, dose-finding study to assess the efficacy, safety, tolerability, PK, and PD of orally administered vadadustat in Japanese subjects with anemia secondary to NDD-CKD. The study will include the following periods: 

• Eligibility screening period (up to 4 weeks)

• Primary efficacy period (6 weeks; Weeks 1 to 6)

• Dose adjustment and maintenance period (10 weeks), including the following:

- Blinded dose adjustment and data cleaning period (4 weeks; Weeks 7 to 10): Individual subject data (from screening to Week 6) will be locked and individual subject unblinding will take place at the Week 10 visit

- Open-label extension period (6 weeks; Weeks 11 to 16): Subjects randomized to receive vadadustat treatment during the blinded period will continue into this period

• Safety follow-up period (2 weeks; Weeks 17 and 18): Subjects who complete

	
participation in the open-label extension period and subjects who discontinue early during the blinded study periods will complete the safety follow-up period. Subjects identified as having received placebo during the Week 10 unblinding visit will not participate in this safety follow-up period.
 
Following the screening period, eligible subjects will be randomized to receive blinded study drug treatment during a 6-week primary efficacy period, with subjects randomized at a 3:1 ratio to receive vadadustat (150, 300, or 600 mg vadadustat) or placebo. See “Dosage and Regimen” in the synopsis for additional information regarding the randomization scheme.
 
Fixed-dose treatment during the blinded primary efficacy period will allow a dose-response relationship to be established. However, if Hb levels increase too rapidly or if the Hb levels exceed the desired range, the blinded study drug dose can be decreased or discontinued (see “Dosage and Regimen” for additional information).
 
After completing the primary efficacy period, subjects will continue to a 10-week dose adjustable maintenance period which will include a 4-week, blinded dose adjustment and data cleaning period and a 6-week, open-label extension period. Dose can be adjusted during the open-label period to achieve a target Hb of 10-12 g/dL, and the dose adjustment guidelines are listed under “Dosage and Regimen” (see below).
 
Individual subject’s study data (from screening to Week 6) will be cleaned and locked during the 4-week, blinded, dose adjustment and data cleaning period.
 
At the Week 10 visit, treatment assignment will be unblinded on an individual subject basis. Subjects who were randomized to receive placebo will end study participation after unblinding at the Week 10 visit. Subjects who were randomized to receive 1 of the 3 vadadustat doses will continue receiving vadadustat during the open-label extension period.
 
Vadadustat treatment will stop after the extension period has been completed (Week 16) and subjects will continue in a 2-week follow-up safety period (Week 17-18).

Study Duration	
Up to 22 weeks, including the eligibility screening period (up to 4 weeks), primary efficacy period (6 weeks), blinded dose adjustment and data cleaning period (4 weeks), open-label extension period (6 weeks), and safety follow-up period (2 weeks).
 
Only subjects who are randomized to receive vadadustat will continue in the maintenance period and the safety follow-up period.

Key Inclusion Criteria (the complete list is provided in the protocol)	
 
Male and female Japanese subjects (20 years or older)
 
Diagnosis of CKD based on an estimated glomerular filtration rate (eGFR) of <math>\leq 60</math> mL/min/1.73 m^2 (using the 2009 Japanese Society of Nephrology equation; Matsuo 2009)
 
Not currently being treated with dialysis and not expected to start dialysis within 3 months of screening
 
Hb <math>\leq 10.5</math> g/dL
 
Serum ferritin <math>\geq 50</math> ng/mL
 
Transferrin saturation (TSAT) <math>\geq 20\%</math>
 
Folate and vitamin B12 <math>\geq</math> lower limit of normal
 

Key Exclusion Criteria (the complete list is provided in the	
Anemia due to a cause other than CKD or presence of active bleeding or recent blood loss; sickle cell disease, myelodysplastic syndromes, bone marrow fibrosis, hematologic malignancy, myeloma, hemolytic anemia, thalassemia, or pure red cell

protocol)	aplasia; red blood cell (RBC) transfusion within 4 weeks prior to or during screening; intravenous iron within 4 weeks prior to or during screening; and any ESA use within 6 weeks prior to or during screening.
Retesting/Rescreening	Subjects who initially fail to qualify for the study based on laboratory test results may be retested once within the screening period, at the investigator's discretion. Subjects who fail to meet the qualifying criteria for Hb or eGFR during screening may be considered for rescreening at the discretion of the investigator, if it is felt that the subject's status has changed and that the subject may now qualify for the study. Additionally, subjects who fail to qualify for the study based on low ferritin, TSAT, folate, or B12 values may be considered for rescreening after receiving replacement therapy. Screening is limited to 3 attempts (initial screening and 2 additional rescreening attempts).
Efficacy Endpoints	
Note that a pre-treatment value for Hb and RBC count is defined as the average of 2 values obtained prior to treatment, ie, the qualifying screening value and the baseline value. Last observation before the first dose of study medication will be used as baseline for other parameters.
 
Primary Endpoint:
 

Mean change in Hb levels from pre-treatment to the end of the primary efficacy period (Week 6)

 
Secondary Endpoints:
 

Proportion of subjects who achieve target Hb 10-12 g/dL at the end of the open-label extension period (Week 16)

Mean change in Hb between pre-treatment and the end of the open-label extension period (Week 16)

Mean change in hematocrit, RBC count, and reticulocyte count from pre-treatment to the end of the primary efficacy period (Week 6) and the end of the open-label extension period (Week 16)

Mean change in iron indices (ie, iron, total iron-binding capacity [TIBC], TSAT, and ferritin) and hepcidin from pre-treatment to the end of the primary efficacy period (Week 6) and the end of the open-label extension period (Week 16)

Proportion of subjects with confirmed Hb values <10.0 or >12.0 g/dL from pre-treatment to the end of the open-label extension period (Week 16)

Proportion of subjects requiring rescue with RBC transfusion from baseline to the end of the primary efficacy period (Week 6) and the end of the open-label extension period (Week 16)

Proportion of subjects requiring rescue with ESAs from baseline to the end of the primary efficacy period (Week 6) and the end of the open-label extension period (Week 16)

Number of dose adjustments from baseline to the end of the primary efficacy period (Week 6) and the end of the open-label extension period (Week 16)

Maintenance of iron sufficiency (defined as ferritin <math>\geq</math>50 ng/mL and TSAT <math>\geq</math>20%) from baseline to the end of the primary efficacy period (Week 6) and the end of the open-label extension period (Week 16)

Plasma concentration profile of vadadustat and its metabolites using pre-dose sample from Week 4

Safety Endpoints	Safety and tolerability assessments, including adverse events, vital signs, electrocardiograms (ECGs), and other laboratory assay results (eg, chemistry,

	components of the complete blood count [CBC] other than the ones noted above, and vascular endothelial growth factor [VEGF])
Dosage and Regimen	
Study drug will be administered on an outpatient basis. Subjects should take the study medication with water or other oral beverage and should be instructed to swallow the intact tablet(s). Subjects may take the study medication with or without food.
 
Note: Hb will be assessed at the central laboratory and also monitored using point-of-care HemoCue®. Note that the point-of-care HemoCue Hb value will be used to determine if the dose of study medication will be adjusted or discontinued.
 
Primary efficacy period (Day 1 to Week 6)
 
Using a central randomization system, subjects will be randomized at a 1:1:1 ratio to receive 1 tablet (150 mg vadadustat or placebo), 2 tablets (300 mg vadadustat or placebo), or 4 tablets (600 mg vadadustat or placebo) of study drug. Within each tablet-count group, subjects will be randomized 3:1 to receive vadadustat or placebo as shown below.
 <pre>graph LR     A[1 tablet (n=16)] --> B[Vadadustat 150 mg (n=12); 1 x 150 mg tablet once daily]     A --> C[Placebo (n=4); 1 tablet once daily]     A --- D[2 tablets (n=16)]     D --> E[Vadadustat 300 mg (n=12); 2 x 150 mg tablets once daily]     D --> F[Placebo (n=4); 2 tablets once daily]     D --- G[4 tablets (n=16)]     G --> H[Vadadustat 600 mg (n=12); 4 x 150 mg tablets once daily]     G --> I[Placebo (n=4); 4 tablets once daily]</pre> 
The primary efficacy period includes a fixed-dose treatment to establish a dose-response relationship. However, if Hb level increases too rapidly or if the Hb levels exceed the desired range, the blinded study drug dose will be decreased or discontinued as presented below.
 

Subjects who meet the following criteria for excess Hb response will undergo a dose reduction by 1 tablet:

Hb increase >1 g/dL within any 2-week period, OR

Hb increase >2 g/dL within any 4-week period, OR

Hb level >13 g/dL

Subjects who meet the following criteria will discontinue study drug:

Excess Hb response as defined by any of the aforementioned criteria, AND

Current dose 1 tablet OR subject had previously decreased study drug dose due to excess Hb response

 
Blinded dose adjustment and data cleaning period (Week 7 to 10)
 
During this period, data from screening through the Week 6 visit will be cleaned and locked in preparation for the Week 10 unblinding visit. Blinded study drug dosage will be adjusted to achieve a target Hb 10-12 g/dL. Starting at the Week 6 visit,


	
adjustments to doses will be based on the dose adjustment guidelines listed below.
 
Open-label extension period (Weeks 11 to 16):
 
Subjects who were randomized to receive vadadustat will enter this open-label extension period, and vadadustat dosage will continue to be adjusted to achieve a target Hb 10-12 g/dL. Dose adjustments will continue to be based on the dose adjustment guidelines listed below.
 
Dose adjustment guidelines from Week 7 to Week 16
 
The dose adjustment for blinded study drug (from Week 7 to 10) and open-label vadadustat (from Week 11 to 16) will follow the dose adjustment guidelines listed below to achieve a target Hb of 10-12 g/dL. The point-of-care HemoCue Hb value will be used to determine if the dose of study drug will be adjusted.
 

• Do not increase the dose more frequently than once within any given 4-week interval. For example, if a subject's dose was increased at Week 10 and the subject remains below the Hb target, the next opportunity to further increase the dose would be Week 14. Decreases in dose can occur more frequently. Avoid frequent dose adjustments.

• If the Hb has not increased by more than 0.5 g/dL above the baseline value after the first 6 weeks of treatment, increase the dose by 1 tablet.

• Increase the dose by 1 tablet every 4 weeks until Hb is above 10.0 g/dL (maximum dose is 4 tablets).

• If the Hb rises rapidly (eg, more than 1 g/dL in any 2-week period), reduce the dose by 1 tablet.

• If the Hb falls below 10.0 g/dL, increase the dose by 1 tablet.

• If the Hb exceeds 12.0 g/dL, reduce the dose by 1 tablet.

• If the Hb exceeds 13.0 g/dL, interrupt study drug until the Hb decreases to 12.5 g/dL or below and then resume dosing with 1 fewer tablet.

• If a dose adjustment is required to maintain Hb at the desired level, the dose adjustment is by 1 tablet.

 
When adjusting therapy, investigators should consider Hb rate of rise, rate of decline, and variability as well as the subject's clinical condition (including recent illness, volume depletion, and volume overload). In cases of extenuating clinical circumstances, investigators may elect to dose outside the dosing guidelines to maintain the Hb within the target range.

Rescue Therapy Guidelines	
The following rescue therapy guidelines are provided to ensure the safety of study subjects and to standardize the use of rescue in the study.
 

• ESA rescue: ESA rescue therapy may be considered based on the investigator's judgment, if a subject:

- Experiences a clinically significant worsening of anemia or symptoms of anemia, and

- Exhibits Hb level <9.0 g/dL

• RBC transfusion: Investigators should use their local institution's transfusion guidelines when determining whether to transfuse a study subject.

 
Subjects who initiate rescue therapy will be required to stop study drug treatment and will be discontinued from the study.

Oral Iron Supplementation	
Subjects who are taking oral iron supplementation at baseline should continue their oral iron at the same dose throughout their study participation. Changes to oral iron supplementation dose will be considered protocol deviations but will not be considered a reason for subject discontinuation.
 
Subjects who are not taking oral iron supplementation at baseline should not start

	
oral iron during their study participation.
 
Important: Because of the potential for oral iron to reduce the bioavailability of vadadustat, study drug (vadadustat or placebo) should not be administered concurrently with any oral iron supplement. Any oral iron supplements (including multivitamins containing iron) should be taken at least 2 hours before or 2 hours after the dose of study drug.

Statistical Considerations	
The primary analysis will use a linear regression analysis to quantify the association between vadadustat dose and mean change in Hb (ie, to assess the vadadustat dose-response relationship). Comparison of each vadadustat dose group versus baseline will be performed. All tests of significance will be performed using a 0.05 two-sided significance level.
 
The target enrollment will be approximately 48 subjects for the study with 12 subjects enrolled in each of the 4 treatment groups. Based on the results from Study AKB-6548-CI-0005 that was conducted in the United States and evaluated vadadustat in patients with anemia secondary to NDD-CKD, the expected mean Hb changes from baseline to Week 6 will be 0, 0.5, 0.7, and 1.2 g/dL for the placebo, 150 mg, 300 mg, and 600 mg vadadustat dose groups, respectively, with a common standard deviation of 0.68 g/dL among the 4 treatment groups. With these assumptions, the study will have >85% power to detect a non-zero slope in a dose-response relationship using linear regression analysis and <math>\alpha=0.05</math>, based on simulation of 10,000 repetitions using SAS® software, Version Number 9.4.

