## 11 DATA ANALYSIS

### 11.1 Primary Endpoint and Sample Size Determination

The primary objective of this study is to quantify the dose-response relationship between oral vadadustat once daily dosing for 6 weeks and change in Hb in Japanese subjects with NDD-CKD in order to define the starting dose for use in Phase 3 clinical studies in Japan.

Change in Hb is defined as the Hb measured at the EOT visit minus the mean pre-treatment Hb. Pre-treatment Hb is defined as the average of 2 Hb values obtained prior to treatment based on the qualifying screening Hb value and the Hb value at the baseline visit. Linear regression analysis will be used to calculate the relationship between vadadustat dose and change in Hb.

The target enrollment will be approximately 48 subjects for the study with 12 subjects enrolled in each of the 4 treatment groups.

Based on the results from Study AKB-6548-CI-0005 that was conducted in the United States and evaluated vadadustat in patients with anemia secondary to NDD CKD, it is reasonable to assume that the expected mean Hb changes from baseline to Week 6 will be 0, 0.5, 0.7, and 1.2 g/dL for the placebo, 150 mg, 300 mg, and 600 mg vadadustat dose groups, respectively, with a common standard deviation of 0.68 g/dL among the 4 treatment groups. With these assumptions, the study will have >85% power to detect a non-zero slope in a dose-response relationship using linear regression analysis and  $\alpha=0.05$ , based on simulation of 10,000 repetitions using SAS® software, Version Number 9.4.

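### The primary regression of Hb change on dose names no covariate; adding pre-treatment Hb is a cheap improvement in precision, not the repair of an error

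*Protocol*

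**What the plan says.** The file holds three successive protocol versions. The last is shown only as far as Section 8.1.4, so Section 11 is read from the version before it. The synopsis wording of the primary analysis is the same in all three.

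- **Model.** Synopsis, Statistical Considerations: "The primary analysis will use a linear regression analysis to quantify the association between vadadustat dose and mean change in Hb". Section 11.1: "Linear regression analysis will be used to calculate the relationship between vadadustat dose and change in Hb". Section 11.5 repeats the regression for Week 6 and extends it to the other red-cell and iron parameters. It also refers back to the primary endpoint analysis as already defined.
- **Response.** Section 11.1: "Change in Hb is defined as the Hb measured at the EOT visit minus the mean pre-treatment Hb". Sections 5.1 and 11.5 name Week 6, and Week 6 is used here.
- **Baseline.** Section 11.1: "Pre-treatment Hb is defined as the average of 2 Hb values obtained prior to treatment based on the qualifying screening Hb value", together with the baseline-visit value. Section 11.2.2 requires this average for entry to the MITT population for Hb.
- **Randomisation.** Sections 6.1 and 8.2.2 describe 1:1:1 allocation to tablet count and then 3:1 to drug or placebo. No stratification factor is named.
- **Planning values.** Mean changes of "0, 0.5, 0.7, and 1.2 g/dL for the placebo, 150 mg, 300 mg, and 600 mg vadadustat dose groups", a "common standard deviation of 0.68 g/dL among the 4 treatment groups", and "12 subjects enrolled in each of the 4 treatment groups".

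**The concern.** Pre-treatment Hb enters the stated model only by subtraction. That is efficient only if a 1 g/dL difference before treatment carries through in full to Week 6. If it does not, because of measurement error, within-subject variation or regression to the mean, the change score stays negatively related to baseline. Part of its variance could then be removed by a covariate that is already collected.

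With 12 per arm and no stratification on Hb, arms can also differ by chance at baseline, and any such relation passes part of the difference into the estimated dose effects. Section 11.1 sets the aim as quantifying dose-response in order to define a Phase 3 starting dose. What is at stake is therefore the precision of the estimate rather than the slope test.

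**Working it through.** **1. The plan's own power figure.** Inputs are the doses 0, 150, 300 and 600 mg, the means and SD above, 12 per arm, and the two-sided 0.05 level from the synopsis.

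- Mean dose is 262.5 mg. Sxx = 12 × (262.5² + 112.5² + 37.5² + 337.5²) = 12 × 196,875 = 2,362,500.
- Expected slope = (−112.5 × 0.5 + 37.5 × 0.7 + 337.5 × 1.2) / 196,875 = 375 / 196,875 = 0.00190 per mg, or 0.190 g/dL per 100 mg.
- SE = 0.68 / √2,362,500 = 0.000442 per mg, or 0.0442 g/dL per 100 mg.
- The ratio is 4.31. On 1 and 46 degrees of freedom the noncentral F gives 98.8% power, and simulation gives 98.6% to 99.0%.

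The stated figure of more than 85% holds as a lower bound.

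**2. Effect of the covariate.** Let r be the correlation between Hb change and pre-treatment Hb within dose. Adjustment multiplies the residual variance by 1 − r². Estimating one more coefficient with N = 48 costs a factor of about 1 + 1/44 = 1.023.

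Net slope-variance ratio = (1 − r²) × 1.023

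This needs no assumption that pre and post variances are equal. Break-even is at r² = 1 − 44/45 = 0.022, so |r| is about 0.15.

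**3. Effect of chance imbalance.** The SE of a between-arm difference in mean change is 0.68 × √(2/12) = 0.278 g/dL. A one-SE imbalance in pre-treatment Hb moves the unadjusted difference in change by |r| × 0.278.

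| Assumed abs(r) | Net variance ratio | Slope SE per 100 mg | Shift from a 1-SE imbalance (g/dL) |
|---|---|---|---|
| 0 | 1.02 | 0.0447 | 0 |
| 0.15 | 1.00 | 0.0442 | 0.04 |
| 0.35 | 0.90 | 0.0419 | 0.10 |
| 0.44 | 0.82 | 0.0402 | 0.12 |

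For scale, the planned step from 150 to 300 mg is 0.7 − 0.5 = 0.2 g/dL.

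**4. Which row applies.** The documents do not say; r, the baseline SD and the pre/post correlation are all assumptions. Simulations with screening Hb truncated at the 10.5 g/dL entry limit, a change SD of 0.68 and assumed variance components gave net ratios of 0.93 to 1.02. A further check that also assumed a degree of persistence of Hb over 6 weeks gave about 0.82 to 1.02. In one unfavourable setting (baseline SD 0.7 of the follow-up SD, pre/post correlation 0.7), the simulated slope SE was 0.0445 unadjusted and 0.0452 adjusted.

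**5. Effect on the test.** With equal pre and post SDs and correlations of 0.9 down to 0.5, adjusted power is 99.1% to 99.8%, against 98.8% unadjusted. In the unfavourable setting of step 4, simulated power is 98.6% unadjusted and 98.4% adjusted. The slope test is essentially unaffected.

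**The case against.** The case for leaving the text alone has four parts.

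- **Silence is not exclusion.** A reader might infer that the protocol fixes an unadjusted model. It does not: no sentence calls the model unadjusted, and a regression with pre-treatment Hb added would satisfy each description. Covariates are commonly left to the SAP, which is not shown. This stands, and it is why the point is a recommendation. It is weakened a little because 11.5 treats the primary analysis as already defined, deferring the full set of efficacy outcomes to the SAP.
- **Baseline is already used.** The response subtracts the mean of two values, which limits what a covariate can add. This stands.
- **The gain may be nil.** A reader might apply the textbook ratio (1 + ρ)/2 and infer a benefit worth 18% (ρ = 0.7) to 33% (ρ = 0.5) more subjects. That needs equal pre and post variances, which the 10.5 g/dL entry limit makes unlikely. The documents do not support those figures.
- **The primary test is sound.** A reader might also infer bias from regression to the mean or from imbalance. Under randomisation, regression to the mean acts equally on all arms in expectation, the unadjusted slope is unbiased, and its SE already allows for chance imbalance. This stands in full.

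What remains is the asymmetry: a possible loss of about 2% of slope variance against a possible gain several times larger, in a trial whose purpose is estimation.

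**Conclusion.** The point holds as a cheap improvement. The stated model names dose only, although a suitable covariate is available for every subject in the MITT population for Hb and nothing described in the design balances it. Adjustment would change the slope variance by between about +2% and about −10% to −18%. In SE terms that is roughly 1% larger to 5-9% smaller (√1.023 = 1.01; √0.90 = 0.95; √0.82 = 0.91). It would also take out the part of any baseline imbalance that carries into the dose estimates, put at 0 to 0.12 g/dL per one-SE imbalance between two arms over the same range.

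These sizes rest on assumed variances and correlations that the protocol does not give. The documents do not establish that a gain will occur, only that the downside is small. Nothing here calls into question the validity or power of the planned slope test.

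**What to change.** In the synopsis, 11.1 and 11.5, state the primary model as Week 6 change in Hb regressed on randomised dose, with pre-treatment Hb (the two-value average) as a covariate. For the secondary regressions in 11.5, use each parameter's own baseline as the covariate.

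The SAP is an acceptable place instead, provided it is final before the first subject is unblinded. Sections 6.1 and 8.2.3 provide for codes to be broken subject by subject after each Week 6 data lock, with unblinding at the Week 10 visit. A covariate chosen later could be chosen with some assignments known.

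The cost is one phrase per place, one of 46 residual degrees of freedom, and at most about 2% of slope variance. No subject is lost from the Hb analysis, since Section 11.2.2 already requires the pre-treatment average. The sample size need not change.
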